10.5 Efficacy Analyses

The efficacy endpoints are ORR, CR, PFS, OS and DOR.

The percentage of subjects with an objective response (CR/ PR) using **the Lugano Classification; and an objective response (CR/ PR) using Revised Response Criteria** during the first 12 weeks since starting blinatumomab (**for part 2 and the cohort in part 1 with selected dose only**) and during the **treatment period** will be summarized with an exact **2-sided** binomial 95% confidence interval **using Full**

Analysis Set. Subjects missing post baseline disease assessments will be considered not to have achieved an objective response.

The KM summaries will be performed for PFS and OS. K-M quartiles along with 2-sided 95% CIs, the number of subjects censored and the number of subjects with events will be provided **using FAS**. The KM summaries of DOR **will** be performed using Responder Analysis Set.

The exploratory endpoint minimal residual disease (MRD) by NGS after cycle 1 of blinatumomab will be summarized with descriptive statistics by treatment cohort using full analysis set.

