Objective response (including CR and PR) by the Lugano Classification is determined by the Lugano Classification (Cheson et al, 2014) during the first 12 weeks since starting blinatumomab and during the treatment period.

Objective Response by the Revised Response Criteria

Objective response (including CR and PR) by the Revised Response Criteria is determined by the Revised Response Criteria (Cheson et al, 2007) during the first 12 weeks since starting blinatumomab and during the treatment period.

Objective Response Rate (ORR) by the Lugano Classification

Objective response rate (ORR) **by the Lugano Classification** is the proportion of subjects who have achieved either a CR or a PR among subjects by **the Lugano Classification (Cheson et al, 2014)** during the first 12 weeks since starting blinatumomab **and during the treatment period** in the respective analysis set.

Objective Response Rate (ORR) by the Revised Response Criteria

Objective response rate (ORR) **by the Revised Response Criteria** is the proportion of subjects who have achieved either a CR or a PR among subjects by **the Revised Response Criteria (Cheson et al, 2007)** during the first 12 weeks since starting blinatumomab **and during the treatment period** in the respective analysis set.

Overall Survival (OS)

The overall survival will be calculated as the time from the date of first dose of blinatumomab until death due to any cause. Subjects who are alive at the date that triggers the analysis will be censored at the date last known to be alive.

Progression Free Survival (PFS) by Lugano Classification

The PFS will be calculated as the time from the date of first dose of blinatumomab until the date of diagnosis of progression of lymphoma, or date of death, whichever is earliest. **For diagnosis of progression of lymphoma, the progression of radiographic assessment of PET-CT using Lugano Classification will be used.** Subjects who are alive and did not have progression will be censored at the last **radiological non-missing evaluable** tumor assessment date.

Progression Free Survival (PFS) by Revised Response Criteria

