7.1 Full Analysis Set

The full analysis set includes all subjects who received blinatumomab.

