10.1 General Principles

The analysis will be performed by cohorts for part 1. The analyses for part 2 will combine subjects in part 2 and the cohort in part 1 with selected dose for part 2 unless specified otherwise. The analyses will be performed on the Full Analysis Set unless specified otherwise.

Continuous variables will be summarized by the non-missing sample size n , mean, standard deviation, median, first and third quartiles, minimum, and maximum.

Categorical variables will be summarized by the n and percentage in each category.

Time to event endpoints will be summarized with hazard ratios, Kaplan-Meier (KM) curves, KM proportions at select time points, KM quartiles (when estimable), the number of subjects with events, the number of subjects censored, and the pattern of censoring.

Point estimates for efficacy endpoints will be accompanied by 2-sided 95% confidence intervals including estimates of KM quartiles (Brookmeyer and Crowley, 1982), KM

proportions (Kalbfleisch and Prentice, 1980), and binomial proportions (Clopper and Pearson, 1934). Pharmacokinetics will be performed by noncompartmental analysis. Pharmacodynamic samples will be summarized by descriptive statistics.

Relationships among drug exposures and efficacy, safety, and biomarkers may be explored if the data are sufficient.

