10.6.13 Exposure Response Analysis

PK data of blinatumomab may be subjected to exploratory population PK analysis with data from multiple studies. Nonlinear mixed effects modeling will be used for the analysis. Effect of covariates on exposure will be determined. These may include, age, body weight, body surface area, renal function, liver function, sex and selected baseline lab values. Other covariates may be analyzed as needed. Individual blinatumomab concentration data at time of interest may be used for the exposure response analysis.

Exposure-response relationships for selected efficacy and safety endpoints may be assessed as appropriate. The objectives and methodology of the exposure-response analysis will be provided in an E-R SSAP.

11. Changes From Protocol-specified Analyses

Because the decision was made not to proceed with Part 2 of the study. The primary analysis will now occur after the last subject in Part 1 has had an opportunity to complete response assessment during first 12 weeks since starting blinatumomab.

Other changes include modifications of the definitions to the following endpoints.

Secondary Endpoint (Per protocol):

Duration of response (DOR) for subjects with OR, (ie, CR and PR) by the Lugano Classification (Cheson et al, 2014) during the first 12 weeks since starting blinatumomab.

Changes from protocol:

Duration of response (DOR) for subjects with OR, (ie, CR and PR) by the Lugano Classification (Cheson et al, 2014) and Revised Response Criteria (Cheson et al, 2007) during the first 12 weeks since starting blinatumomab.

PFS definition (Per protocol):

The PFS will be calculated as the time from the date of first dose of blinatumomab until the date of diagnosis of progression of lymphoma, or date of death, whichever is earliest. For diagnosis of progression of lymphoma, the progression of radiographic assessment of PET-CT using Lugano Classification will be used. Subjects who are alive and did not have progression will be censored at the last radiological non-missing evaluable tumor assessment date. Progression free survival for subjects who were enrolled in dose cohorts that were not selected for the extension cohort will not be calculated.

Changes from protocol:

Progression Free Survival (PFS) by Lugano Classification:

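### SAP 10.5 restricts the 12-week objective response summary to Part 2 and the selected-dose cohort, but SAP 11 cancels Part 2 and no cohort is named as selected

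*SAP*

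**What the plan says.** SAP 10.5 asks for the percentage of subjects with an objective response, with an exact two-sided 95% interval, by each of two criteria and in two windows. The treatment-period window carries no cohort limit. The 12-week window does: "for part 2 and the cohort in part 1 with selected dose only". The same sentence names the Full Analysis Set, defined in SAP 7.1: "The full analysis set includes all subjects who received blinatumomab".

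SAP 11 opens its list of changes with "Because the decision was made not to proceed with Part 2 of the study" and continues: "The primary analysis will now occur after the last subject in Part 1 has had an opportunity to complete response assessment during first 12 weeks".

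SAP 10.1 has two general rules. For Part 1: "The analysis will be performed by cohorts for part 1". For Part 2: "The analyses for part 2 will combine subjects in part 2 and the cohort in part 1 with selected dose for part 2".

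SAP 6.2 says that the response rate "is the proportion of subjects who have achieved either a CR or a PR among subjects by" each set of criteria, within the respective analysis set, and puts no limit on cohort. Protocol 10.4.2.2 likewise plans the 12-week rate and exact interval without a cohort limit, and protocol 10.4.1 has Part 1 analysed by cohort.

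**The concern.** The limit in SAP 10.5 points to two populations. One will not exist. The other is the Part 1 cohort at the dose selected for Part 2, and with Part 2 cancelled the SAP does not say whether any dose counts as selected, or which.

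The words look like a leftover. They repeat the SAP 10.1 pooling rule for Part 2 analyses and add *only*, which turns a rule about whom to combine into a rule about whom to leave out. SAP 11 deals with the parallel case: it cites the protocol 10.1.1.2 statement that progression-free survival is not calculated for unselected cohorts, and gives a revised definition without it. The response limit was not revisited.

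At stake is a stated secondary endpoint. The primary analysis is now timed on the 12-week response assessment of the last Part 1 subject, yet the section that specifies the 12-week response table excludes most or all Part 1 cohorts.

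**Working it through.** The plan gives no figure for this point, so the check compares the texts and then counts summaries.

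**1. Which cohorts does the limit admit?**

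| Source | Effect on 12-week response |
|---|---|
| SAP 10.5 | Part 2 and the selected-dose Part 1 cohort, no others |
| SAP 11 | Part 2 does not happen; no cohort named |
| SAP 10.1 | Selected dose means the dose selected for Part 2; Part 1 is analysed by cohort |
| Protocol 10.4.2.2 | No cohort limit |

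If no dose was selected for Part 2, 0 cohorts qualify. If the recommended dose is treated as selected, 1 does.

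**2. How many summaries are due, and how many are produced?** SAP 3.1 allows up to 3 dose cohorts in Part 1, and there are 2 sets of criteria.

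- Due = cohorts × 2
- Produced under the literal text = 0 × 2 = 0, or 1 × 2 = 2
- Missing = due − produced

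| Cohorts opened | Due | Missing if none selected | Missing if one selected |
|---|---|---|---|
| 1 | 2 | 2 | 0 |
| 2 | 4 | 4 | 2 |
| 3 | 6 | 6 | 4 |

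**3. What would one missing summary look like?** As assumed data only, take the minimum response counts that SAP 3.1 requires for moving to Part 2. The Clopper-Pearson limits for x responders among n subjects are the 0.025 quantile of Beta(x, n − x + 1) and the 0.975 quantile of Beta(x + 1, n − x).

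- 1 of 6: 16.7%, 95% CI 0.4% to 64.1%
- 2 of 10: 20.0%, 95% CI 2.5% to 55.6%

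**4. Can it be rebuilt?** Duration of response is summarised on the Responder Analysis Set (SAP 7.3), which is all 12-week responders with no cohort limit. SAP 10.1 has time-to-event summaries report "the number of subjects with events, the number of subjects censored, and the pattern of censoring". So, for each cohort, x = duration-of-response events + censored subjects, and n = the cohort's Full Analysis Set count. The interval follows from x and n.

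**5. Does treatment-period response stand in?** Protocol 7.3.12.3 schedules the first scan at Day 64 and later ones every 12 weeks, so the second is due at 64 + 84 = Day 148. Day 64 is the only routine scan within the 84-day window, and a first response at Day 148 counts in the treatment-period rate but not in the 12-week rate. A mismatch the other way is possible too: SAP 6.1 ends the treatment period 30 days after the last dose, so a subject last dosed before Day 34 (64 − 30) and scanned on Day 64 is inside the 12-week window but outside the treatment period.

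**The case against.** The strongest reply is that little information is lost. As step 4 shows, the responder count and denominator can be recovered for each cohort, and treatment-period response is tabulated for all cohorts anyway. The count of missing summaries is a count of table entries and depends on how many cohorts opened, which the documents do not give. Intervals as wide as those in step 3 would inform little.

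A second reply is that a selected-dose restriction suits the design. The protocol sizes Part 2, not Part 1, for response estimation, and itself limited progression-free survival to the selected cohort. The review team's records may also identify the selected dose even though the SAP does not. A third is that the by-cohort rule in SAP 10.1, read with the new timing in SAP 11, tells a programmer what is meant.

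Much of this stands as a limit on the size of the problem. Naming the Full Analysis Set does not by itself require a table for every cohort, and neither does an endpoint definition without a cohort limit; both are supporting evidence of intent only. But the core is untouched. SAP 10.5 is the specific instruction and says *only*. In SAP 10.1 the allowance for exceptions is attached to the pooling and analysis-set sentences, not to the by-cohort sentence, so the two sections give different answers. If the restriction was a deliberate choice, it departs from protocol 10.4.2.2 and belongs in SAP 11, where it does not appear. Having readers rebuild a planned secondary result from another endpoint's event counts is no substitute for tabulating it.

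**Conclusion.** The point holds. As written, SAP 10.5 does not produce the by-cohort 12-week response summary that SAP 10.1 and protocol 10.4.2.2 call for. The loss is 4 or 6 of 6 summaries with three cohorts, 2 or 4 of 4 with two, and 0 or 2 of 2 with one. This assumes that SAP 10.5 is followed literally; the number of cohorts opened, and whether any dose is regarded as selected, are not stated.

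The consequence is bounded. Dose-limiting toxicity, treatment-period response, progression-free survival, overall survival and duration of response are unaffected, and the missing counts can be recovered. It should still be corrected before the analysis, because it changes what is reported for a stated secondary endpoint.

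**What to change.** In SAP 10.5, delete the parenthesis, so that 12-week objective response under both criteria is summarised for every Part 1 cohort on the Full Analysis Set with exact 95% intervals, following the by-cohort rule in SAP 10.1. Add a line to SAP 11 beside the change to progression-free survival.

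If the sponsor wants to keep the restriction, SAP 10.5 should name the cohort and SAP 11 should list it as a change from protocol 10.4.2.2.

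The cost is one deletion, one added line and, at most, extra columns in one table. No new data are needed, since 12-week response must be derived for every cohort in any case to form the Responder Analysis Set.

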10.6 Safety Analyses

10.6.1 DLT Summary

The DLT criteria are defined in the Appendix E of the protocol.

Incidence rates of DLTs and corresponding exact binomial 95% CIs will be summarized for DLT evaluable subjects.

10.6.2 Adverse Events and Disease Related Events

The Medical Dictionary for Regulatory Activities (MedDRA) version 22.1 or later will be used to code all events categorized as adverse events (AEs) or disease-related events (DREs) to a system organ class and a preferred term. AEs of interest (EOI) categories will be based on search strategies defined by Medical Coding. **Treatment emergent adverse event refers to an adverse event that starts on or after first dose of blinatumomab up to and including 30 days after the end of blinatumomab or pembrolizumab whichever is later.**

Subject incidence of all, serious, grade 3 and above, leading to withdrawal of investigational product, leading to interruption of investigational product, fatal, treatment-related, **treatment-related serious, and treatment-related grade 3 and above** treatment-emergent adverse events (**including DREs**) will be tabulated by system organ class and preferred term in descending order of frequency **for highest dose group**.

Treatment-emergent events of interest (EOIs) will be summarized by EOI category and preferred term. In addition, for each EOI category, the subject incidence of all, serious, **grade 3 and above, grade 4 and above**, fatal, leading to withdrawal of investigational product, leading to interruption of investigational product will be summarized. **Time to onset, duration, number of selected EOIs will also be summarized.**

Additionally, treatment emergent DREs and fatal DREs will be summarized by system organ class and preferred term in descending order of frequency **for highest dose group**. Subject incidence of ECIs will be summarized by ECI category and preferred term in descending order of frequency **for highest dose group**.

Subgroup analyses of treatment-emergent adverse events will be presented for age-group (< 65, 65-74, ≥ 75), and gender by system organ class and preferred term in descending order of frequency for highest dose group.

Subject listings of Serious AEs, Fatal AEs and Deaths will be provided. Analyses will be performed based on Safety Analysis Set.

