cohort Ia, and on study day 19 in cohorts IIa and IIIa. Trial treatment of pembrolizumab may be administered up to 3 days before or after each scheduled day (**calculated from day 1**) from pembrolizumab cycle 2 onwards.

Subjects who do not meet the criteria for investigational product discontinuation (see below) are eligible for a second cycle of blinatumomab (consolidation) consisting of a CIVI of 28 days after a 28-day (± 3 days) blinatumomab treatment-free interval. Blinatumomab will be started at 9 $\mu\text{g}/\text{day}$ and escalated every 7 days to the maximum target dose of blinatumomab in the assigned cohort.

Subjects will be enrolled to part 1 with up to 6 subjects being enrolled per cohort. In any cohort, tolerability will be defined as ≤ 1 DLT out of 6 subjects. Expansion to 10 subjects will be allowed in any cohort to ensure adequate safety and PK data is collected. The decision to expand a cohort will be made by the DLRT. In case of 10 subjects enrolled, tolerability is defined as ≤ 2 DLTs out of 10 subjects.

The MTD of blinatumomab will be defined as the highest dose level at which at most 1 of 6 subjects or at most 2 subjects in 10 experiences a DLT. The MTD defines the stopping rules for the study. For further details on replacement of subjects, please see Section 3.4. For DLT criteria, please see [Appendix E](#).

The DLRT will meet to review the safety data when any of the following criteria are met:

- In 2 or more subjects out of 6, a DLT has been reported, or in 3 or more subjects out of 10, a DLT has been reported in a cohort
- Six subjects are enrolled in a cohort and all subjects have completed the DLT observation period.
- In the event that a cohort is expanded to 10, DLRT will also meet after all subjects have completed DLT observation period.

The DLRT will review the available data in part 1 to determine if the combination of blinatumomab and pembrolizumab is safe and tolerable as defined by DLT criteria. Based on the totality of the data, the DLRT may recommend to declare MTD, to escalate to the next dose level, to expand a cohort to a maximum of 10 subjects if the collection of more data is deemed warranted, or to adjudicate the DLT criteria (see [Appendix E](#) for details). At the end of Part 1, the cohort with recommended dose level requires to have at least 1 response out of 6 evaluable subjects or 2 responses out of 10 evaluable subjects to proceed to Part 2.

Part 2

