For part 1, subject enrollment will start in cohort Ia as outlined in the schema in [Figure 1](#). Blinatumomab will be dosed as a continuous intravenous infusion (CIVI) for 8 weeks. The initial dose will be 9 $\mu\text{g}/\text{day}$ and the dose will be escalated after 7 days to a target dose of 28 $\mu\text{g}/\text{day}$. Depending on tolerability, the target dose of blinatumomab will be increased to a maximum of **56** $\mu\text{g}/\text{day}$ in cohort IIa **or** to **112** $\mu\text{g}/\text{day}$ in cohort IIIa. Pembrolizumab will be dosed by intravenous (IV) infusion 200 mg at Q3W starting on study day 15 in cohort Ia, and on study day 19 in cohorts IIa and IIIa. Trial treatment of pembrolizumab may be administered up to 3 days before or after each scheduled day 1 from pembrolizumab cycle 2 onwards.

Subjects who do not meet the criteria for investigational product (IP) discontinuation (see below) are eligible for a second cycle of blinatumomab (consolidation) consisting of a CIVI of 28 days after a 28-day (± 3 days) blinatumomab treatment-free interval. Blinatumomab will be started at 9 $\mu\text{g}/\text{day}$ and escalated every 7 days to the maximum target dose of blinatumomab in the assigned cohort.

Subjects will be enrolled to part 1 with up to 6 subjects being enrolled per cohort. In any cohort, tolerability **will be defined as ≤ 1 DLT out of 6 subjects**). **Expansion** to 10 subjects **will be allowed in any cohort** to ensure adequate safety and PK data is

collected. The decision to expand a cohort will be made by the DLRT. **In case of 10 subjects enrolled, tolerability is defined as ≤ 2 DLTs out of 10 subjects.**

The MTD of blinatumomab will be defined as the **highest** dose level at which at most 1 of 6 subjects **or at most 2 subjects in 10** experiences a DLT. The MTD defines the stopping rules for the study. For further details on replacement of subjects is given in Section 3.4 of protocol. The DLT criteria are defined in the Appendix E of the protocol.

The DLRT will meet to review the safety data when any of the following criteria are met:

- In two or more subjects **out of 6, a DLT has been reported, or 3 or more subjects out of 10, a DLT** has been reported in a cohort.
- Six subjects are enrolled in a cohort and all subjects have completed the DLT observation period.
- In the event that a cohort is expanded to 10, DLRT **will** also meet after all subjects have completed DLT observation period.

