Relative dose intensity at the target dose is the actual exposure duration at target dose divided by planned duration of target dose, which is 49 days for cohort Ia, and 42 days for cohort IIa and IIIa in cycle 1; and 21 days for cohort Ia, and 14 days for cohort IIa and IIIa in cycle 2. Subjects who didn't reach the target dose are considered having actual exposure duration as 0.

Study Day

Study Day 1 is defined as the day of first dose of blinatumomab.

And Study Day is defined as:

Pre study day 1: study day= (date – date of study day 1)

Post study day 1: study day= (date - date of study day 1) + 1

Subject Level End of Study (EOS) Date

End of Study for each subject is defined as the date the subject last completed a protocol-specified procedure. The date will be recorded on the End of Study CRF page.

Treatment Emergent Adverse Event (AE)

Treatment emergent adverse event refers to an adverse event that starts on or after first dose of blinatumomab up to and including 30 days after the end of blinatumomab or pembrolizumab whichever is later. It is indicated by a flag whether an event start before first dose of blinatumomab on the Event CRF page. This reporting window also applies to treatment-emergent serious adverse events (SAEs).

Treatment Emergent Disease-related Event (DRE)

Treatment emergent disease-related event refers to a disease-related event that starts on or after first dose of blinatumomab up to and including 30 days after the end of blinatumomab or pembrolizumab whichever is later. It is indicated by a flag whether an event start before first dose of blinatumomab on the Event CRF page.

Disease-related events assessed by the investigator to be more severe than expected and/or related to the investigational product(s)/study treatment/protocol-required therapies, and determined to be serious, must be reported on the Event CRF as serious adverse events.

Treatment Emergent Event of Clinical Interest (ECI)

ECI is defined in Section 9.1.4 of the protocol. Treatment emergent ECI refers to an ECI that starts on or after first dose of blinatumomab up to and including 30 days after the end of blinatumomab or pembrolizumab whichever is later.

Primary Completion: The primary completion date is defined as the date when the last subject is assessed or receives an intervention for the final collection of data for the primary endpoint(s), whether the study concluded as planned in the protocol or was terminated early.

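### At the primary analysis, crude adverse event incidence by cohort may understate later-onset and consolidation-cycle events in the last-enrolled cohort

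*SAP*

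**What the plan says.** - **Reporting unit.** SAP 10.1: "The analysis will be performed by cohorts for part 1".
- **Statistic.** SAP 10.6.2 gives the subject incidence of all, serious, grade 3 and above, and other categories of treatment-emergent event. These "will be tabulated by system organ class and preferred term in descending order of frequency", with the sort order taken from the highest dose group. I read that as dose groups shown side by side.
- **Counting window.** Under SAP 6.1 an event counts if it "starts on or after first dose of blinatumomab up to and including 30 days after the end of blinatumomab or pembrolizumab whichever is later". Pembrolizumab may run to 35 cycles.
- **Order of cohorts.** SAP 3.1: "For part 1, subject enrollment will start in cohort Ia as outlined in the schema". The target dose then rises depending on tolerability. One trigger for the dose level review in Protocol 3.1 is that "Six subjects are enrolled in a cohort and all subjects have completed the DLT observation period"; the other early trigger is an excess of DLTs.
- **Timing of the cut.** SAP 11 records that Part 2 will not go ahead and places the primary analysis "after the last subject in Part 1 has had an opportunity to complete response assessment during first 12 weeks since starting blinatumomab".

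The plan also summarises duration of therapy (SAP 10.6.8) and time to onset for selected events of interest (SAP 10.6.2), and it covers a final analysis (SAP 1). No general adverse event table uses a fixed window or time at risk. By contrast, SAP 10.5 gives response a 12-week window, and PFS and OS Kaplan-Meier summaries.

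**The concern.** Crude incidence can be compared across cohorts only if subjects are observed for similar lengths of time. Here the cut is tied to the last subject enrolled, and cohorts enroll in dose order. The last cohort is therefore read at an earlier point in its treatment than the others.

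Two kinds of event are exposed. Protocol 6.2.2.2.2 says immune-related events may appear several months after the last pembrolizumab dose. The consolidation cycle is a second start of blinatumomab at 9 µg/day with weekly steps, and the last subject may not have reached it at the cut. With Part 2 cancelled, these tables are the main evidence on dose and toxicity beyond the 42-day DLT count.

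**Working it through.** **1. The plan's own schedule.** Cycle 35 falls on day 15 + 34×21 = 729 in Ia and 19 + 34×21 = 733 in IIa/IIIa. Adding 30 days gives 759 and 763, as in Protocol Tables 7-2 and 7-4. The counting window can therefore exceed two years.

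**2. Minimum potential follow-up at the primary cut.** The DLT period ends at about day 15 + 42 = 57 (Ia) or 19 + 42 = 61 (IIa, IIIa). I assume that all three cohorts open in order, each after review of the one before, with no accrual or review time:
- IIIa: 84 days
- IIa: 61 + 84 = 145 days
- Ia: 57 + 61 + 84 = 202 days

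Pembrolizumab doses scheduled by then are 9 in Ia (day 183 is the ninth, day 204 the tenth) and 4 in IIIa (days 19, 40, 61, 82). Consolidation is scheduled for days 85 to 113. It would be over for eligible Ia and IIa subjects and not yet begun for a IIIa subject at day 84.

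**3. Effect on crude incidence when true risk is equal at every dose.** The observed window is the smaller of (treatment duration + 30 days) and potential follow-up. Incidence is 1 − E[exp(−cumulative hazard over the window)], by Monte Carlo. The documents give no accrual, treatment duration or event hazard, so the following are assumptions:
- accrual span per cohort of 0 or 90 days;
- exponential treatment duration with the median shown;
- a hazard of 10% per 84 days, either constant or starting at day 61, or a 30% front-loaded hazard with mean onset about 21 days.

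Each cell is Ia / IIIa.

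| Median treatment, accrual span | Mean window (days) | Constant | After day 61 only | Front-loaded |
|---|---|---|---|---|
| 60 d, 0 d | 105 / 70 | 12.1% / 8.4% | 5.7% / 1.7% | 29.2% / 29.1% |
| 60 d, 90 d | 116 / 88 | 13.1% / 10.3% | 6.8% / 3.8% | 29.3% / 29.2% |
| 180 d, 0 d | 156 / 79 | 17.5% / 9.4% | 11.2% / 2.4% | 30.0% / 29.7% |
| 180 d, 90 d | 233 / 111 | 24.2% / 13.0% | 18.4% / 6.3% | 30.0% / 29.9% |
| 365 d, 0 d | 177 / 81 | 19.7% / 9.7% | 13.5% / 2.6% | 30.2% / 29.8% |
| 365 d, 90 d | 308 / 120 | 31.0% / 13.9% | 25.6% / 7.1% | 30.2% / 30.1% |

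Under the constant hazard, the IIIa hazard could be about 1.3 to 2.5 times that of Ia and still show the same crude incidence. The front-loaded column has a single early peak, so it covers first-cycle events but not consolidation.

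**4. With a common 84-day window.** Under the constant 10% hazard, Ia and IIIa agree: 8.4%, 8.9%, 9.4% and 9.7% for median treatment of 60, 90, 180 and 365 days.

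**5. Would person-time rates do instead?** Take 30% true incidence in both cohorts, mean onset at day 21, and windows of 202 and 84 days. Per 30-day month:
- Ia: 30 × 0.3/(0.3×21 + 0.7×202) = 30 × 0.3/147.7 = 0.061
- IIIa: 30 × 0.3/(0.3×21 + 0.7×84) = 30 × 0.3/65.1 = 0.138

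That is a false 2.3-fold excess in the shorter-followed cohort.

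**The case against.** A reader might infer that the highest dose will look safer than it is across adverse events generally. The documents do not support that.

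- **Most blinatumomab events are early.** Protocol 2.4 says they cluster around initiation and dose steps. It cites median onsets of 18 days for grade 3 or higher neurologic events in one study and 2 days for grade 3 CRS in another. Every cohort's first step-up falls well inside 84 days. This stands for cycle 1, but not for the second step-up in consolidation.
- **Observation often ends before the cut.** Counting stops 30 days after the last dose, progression generally ends treatment, and the first scheduled scan is day 64. Protocol Table 2-2 lists PFS of 49 days, 83 days, 1.6 months and 2.5 months for some other agents. Early discontinuation narrows the gap. With median treatment of 60 days in Ia and 365 in IIIa (90-day span), the constant-hazard order reverses, 13.1% against 13.9%.
- **The last cohort need not be the highest dose.** Any cohort may be expanded to 10. Late expansion of a lower one can narrow or reverse the gap.
- **The imbalance is partly visible and temporary.** Duration of therapy and onset of selected events are reported, and at the final analysis the windows are no longer cut short. But duration is never used with the incidence tables, and the final analysis waits until about 24 months after the last pembrolizumab dose.
- **The main decision is untouched.** DLTs have a fixed 42-day window, and no formal cross-cohort adverse event comparison is planned.

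All of this limits the point. It does not make the full-period tables comparable for later events at the primary cut.

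**Conclusion.** The point holds in a limited form. If cohorts open in sequence, the last-enrolled cohort has at least 84 days of potential follow-up at the primary analysis, against 145 (IIa) and 202 (Ia). Later-onset immune-related events and consolidation-cycle events may therefore be understated there relative to earlier cohorts. First-cycle blinatumomab events and the DLT endpoint are essentially unaffected, and the final analysis largely resolves the difference.

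The follow-up minimums rest on the documents plus the assumption that cohorts open in order with no accrual or review time. The incidence figures rest on assumed accrual, treatment duration and hazards. Nothing applies if only one cohort was run.

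It is tempting to say that a 30% incidence at 84 days becomes 58% at 202 days, since 1 − 0.7^(202/84) = 0.576. That needs a constant hazard and nobody stopping treatment, so it is only an upper-end illustration for these minimum windows and should not be cited as the expected effect.

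**What to change.** In SAP 10.6.2, for the primary analysis:

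1. Add by-cohort tables of all, serious and grade 3 or higher treatment-emergent events, and of events of interest, limited to onset within 84 days of the first blinatumomab dose. Base cross-cohort statements on these.
2. Keep the full-period crude tables, shown with each cohort's observation time and the number of subjects who started cycle 2. State that later-onset and cycle 2 events are not comparable across cohorts at this cut.
3. If exposure-adjusted rates are shown, label them supportive only, because they mislead for front-loaded events.

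The cost is SAP wording and a date filter on existing table programs, with no new data. The downside is a few more tables with small numbers per cohort. The 84-day window also excludes cycle 2 and most late events, so those remain without a fair cross-cohort comparison until the final analysis.
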